5.1.2 Assessment of efficacy

The primary efficacy endpoint data will be assessed by analysis of changes in the patient-reported FVC over time and comparison with the clinicmeasured FVC at beginning and end of the study, clinic-derived parameters and health outcomes over time.

The secondary efficacy endpoint data will be assessed by analysis of changes in the patient-reported health parameters (including PROMs) over time and comparison with clinic-derived parameters and health outcomes over time (described above in 5.1.1.2).

The acceptability and utility of the patientMpower app will be assessed by analysis of the responses to the patient and healthcare professional questionnaires (described above in 5.1.1.2).

5.2 Safety

It is not anticipated that any safety issues will arise from use of the patientMpower app or the Spirobank Smart spirometer.

Any adverse events (AEs) observed in patients who have received medical treatments should be reported to the manufacturers of those treatments. The process for reporting AEs is described in section 8.4 and further information on the definitions of and reporting requirements of AEs is given in Appendix 10.3.

There are no safety endpoints in this study.

5.3. Other variables

Demographic data (date of birth, gender, date of IPF diagnosis, other respiratory conditions, medication prescribed for IPF or respiratory conditions).

Type of smartphone or tablet device (i.e. iPad or Android tablet, iPhone or Android phone)

Engagement of patients with the patientMpower app will be assessed by analysis of the numbers of

- patients asked to take part in the study
- patients who give informed consent to take part in the study.
- consented patients who download the app application to their smartphone or tablet device
- patients who use the app at least once after downloading
- patients who use the app more than once
- frequency of use by each patient
- date intervals between informed consent, download, first use
- date intervals between first and subsequent uses
- frequency of recording FVC at home
- frequency of recording PROM at home
- frequency of recording other measures at home

5.3.2 Other assessments

Data on the air quality at the patients' geographical location can be made available to them via the patientMpower app during the study. It is possible that these data may be analysed retrospectively to see if there is any correlation between air quality and impact of IPF on patient quality of life, respiratory measurements or exacerbations.

Data on the ultraviolet index at the patients' geographical locations over the duration of the study may be captured. These data may be analysed retrospectively to see if there is any correlation between possible ultraviolet exposure and impact of IPF on patient quality of life or possible side-effects of IPF treatment.

5.4 Appropriateness of measurements

The primary endpoint parameter FVC is an important measure of disease severity in IPF and a decline in FVC is consistent with disease progression [1, 15].

The secondary endpoint parameters are measurements which are affected by the patient's IPF and respiratory health.

The questionnaires used to assess usefulness and patient acceptability have been used to assess these parameters for other patient support platforms.

6 Investigational plan

Patients who participate in the study will follow their usual care programme and will be encouraged to use the patientMpower app and MIR Spirobank Smart spirometer every day to record parameters relevant to their health status (described in section 5.1.1.2 above).

6.1 Visit schedule

The total observation period will be sixteen $(16) \pm eight (8)$ weeks. This time interval coincides with the interval between usual clinic visits.

6.2 Details of study procedures at all visits

6.2.1 Patient recruitment process

The patient recruitment process is summarized in the flow-chart 1 on page 6 and in Figure 1 on page 10.

At a usual care visit to the study centre, the research team will discuss the study with the patient (face-to-face), confirm their understanding of the study processes and their willingness to participate. During the informed consent discussion, it will be made clear to the patient that their identity and email address will be made known to patientMpower Ltd and that data collected on the app will be stored and analysed by patientMpower Ltd.

Written informed consent will be obtained before any study-specific procedures and before installation of the patientMpower app.

The study starts at this visit (baseline visit).

After the patient has given written informed consent to participate, the study centre will advise patientMpower Ltd. of the email address of patient and that they have consented to participate.

patientMpower Ltd. will send an information pack via e-mail to the patient. This will include instructions on installation of the patientMpower app and Bluetooth pairing of the spirometer. patientMpower will also send a MIR Spirobank Smart spirometer to the patient. These will be sent to the patient within two working days of the baseline visit.

If requested by the patient, patientMpower Ltd will contact them to offer help with installation of patientMpower app and pairing of spirometer.

6.2.2 Baseline clinic visit

The study procedures and assessments during the observation period at each clinic visit are summarized in flow-chart 2 on page 7.

At a usual care visit to the study centre, the research team will discuss the study with the patient (face-to-face), confirm their understanding of the study processes and their willingness to participate.

Written informed consent will be obtained before any study-specific assessments and before installation of the patientMpower app.

The study starts at this visit.

The patient will be instructed in the correct use of the Spirobank Smart home spirometer and uploading of data to the patientMpower app. The patient's understanding of the patientMpower app, Spirobank Smart home spirometer and the study procedures should be checked before they leave the clinic.

Demographic data, medical history and concomitant therapy for IPF and other respiratory conditions will be recorded.

The following parameters will be assessed and recorded in the clinic records:

- spirometry (to include FVC)
- dyspnoea (e.g. UCSD Shortness of Breath Questionnaire or other measure usually used by the investigator sites) impact of IPF on daily life (using the same PROM as in the patientMpower app)

The study centre will advise patientMpower Ltd that the patient has consented to participate in the study and provide the patient's contact details.

patientMpower Ltd. will send the patient an information pack (via email) and a home spirometer (via regular mail or courier). The information pack will give instructions (including video clips) on how to install the patientMpower app onto your smartphone or tablet device and how to pair the spirometer with the app. During the installation, some information on the patient (e.g. date of birth and gender) will be recorded on the patientMpower app. If necessary, the patient may be loaned a tablet device (like an iPad) which will have the patientMpower app installed. If requested by the patient, patientMpower Ltd. will provide technical support to the patient in downloading the app and pairing with the spirometer.

6.2.3 Treatment and observation period

Patients will be encouraged to record the parameters described in section 5.1.1.1 and 5.1.1.2 on a regular basis.

The following should be recorded by the patient each day:

- FVC (one spirometry manoeuvre each day ideally at approximately the same time each day but this is not essential)
- compliance with medication prescribed for IPF (if prescribed)
- any changes to medication taken for IPF
- activity (number of steps per day)
- distance walked per day
- maximum level of dyspnoea

Impact of IPF on daily life (PROM) should be recorded by the patients every week.

Patients will receive reminders (via the patientMpower app) at appropriate intervals to record study parameters.

Other parameters should be recorded by the patient (if suitable measurement devices are available to the patient and where practical for the patient) frequently. Examples include duration of walking, number of episodes of walking, cough, heart rate, blood pressure, temperature, body weight, oxygen saturation and oxygen usage (e.g. cylinders/month).

If requested by the patient, patientMpower Ltd will provide technical support on correct use of the app or spirometer at any time during the study.

6.2.4 End of treatment clinic visit (16 \pm 8 weeks) and follow-up period

The following parameters will be assessed and recorded in the clinic records:

- spirometry (to include FVC)
- dyspnoea (e.g. UCSD Shortness of Breath Questionnaire or other measure usually used by the investigator sites)
- impact of IPF on daily life (using the same PROM as in the patientMpower app)
- medication adherence (if prescribed for IPF)
- changes in or addition of any new medicines for the treatment of IPF (if prescribed)
- exacerbations of IPF since previous visit
- hospitalisations due to IPF since previous visit

The patient and healthcare professional opinion on the usefulness and acceptability of the patientMpower app will be assessed and recorded. (The questions are described in section 5.1.1.2 above.)

7. Statistical methods and determination of sample size

This a pilot study to assess the feasibility of patients with IPF using the patientMpower app including home-based FVC to monitor their health.

7.1 Statistical design and model

Open-label, single-arm observational study.

7.2 Null and alternative hypotheses

Not relevant.

7.3 Planned analyses

Results will be collected and summarized for descriptive statistical display.

7.3.1 Primary analyses

The primary efficacy endpoint will be assessed by analysis of changes in patient-reported FVC, clinic-derived parameters and health outcomes over time.

The patient-reported FVC will be compared with the clinic-derived measures and health outcomes to determine if there are any correlations between them.

7.3.2 Secondary analyses

The secondary efficacy endpoints data will be assessed by analysis of changes in the patient-reported health parameters, clinic-derived parameters and health outcomes over time.

The patient-reported health parameters and will be compared with the clinicderived measures and health outcomes to determine if there are any correlations between them.

The acceptability and utility of the patientMpower app will be assessed by analysis of the responses to the patient and healthcare professional questionnaires (described above in 5.1.1.2).

7.3.3 Safety analyses

None planned.

7.3.4 Interim analyses

None planned.

7.3.5 Health economic analyses

Health outcomes (e.g. exacerbations of IPF) will be recorded.

7.4 Handling of missing data

No imputations of missing data will be made.

7.5. Randomisation

Not relevant.

7.6 Determination of sample size

This is pilot study. The proposed sample size of 25 subjects has been chosen arbitrarily.

8. Informed consent, data protection and study records

8.1 Study approval, patient information and informed consent

The study will be approved by the relevant ethics committee(s) for the participating centre.

The study will be discussed with each patient and they will be provided with written information (both electronic and paper) describing the study conditions and procedures.

All patients will give electronic written informed consent before participation.

8.2 Data quality assurance

All endpoint data will be stored on a central database for analysis. The data as reported by the patients will not be queried before descriptive statistical analysis tables are prepared.

8.3 Records

8.3.1 Source documents

The original electronic data recorded in the patientMpower application will be the source document.

8.3.2 Direct access to source data and documents

Source data verification will not be performed.

8.3.3 Storage of records

Medical data relating to patient care will be stored in the medical records according to the usual procedures of the investigator sites.

The endpoint data collected by the participants and recorded on the patientMpower app will be stored in a secure cloud database managed by patientMpower Ltd. These data will be available to patients indefinitely to aid them in self-management of their medical condition. Patients can request deletion of their data from the patientMpower cloud database at any time.

8.4 Reporting of adverse events

An AE is defined as any untoward medical occurrence in a patient or clinical investigation subject administered a medicinal product and which does not necessarily have a causal relationship with this treatment. An AE can therefore be any unfavourable and unintended sign (e.g. an abnormal laboratory finding), symptom, or disease temporally associated with the use of a medicinal product, whether or not considered related to the medicinal product.

All observed AEs must be reported to the manufacturers of the medicinal product(s) administered (irrespective of causal relationship).

The patientMpower app contains a journal entry page where a patient can enter information from a list of pre-defined symptoms (e.g. cough) or can enter free text (e.g. "nausea") in example screenshot shown below in Figure 8.4: 1. Therefore, it is possible that the patient can record AEs which may or may not be related to drug treatment.

Figure 8.4: 1 Screenshot of journal entry page:

÷	Add Journa	I Entry		SAVE
	2017-12-11	\bigcirc	15:48	
naus Cough				
Ģ	Add a ph	oto (e.g. r	ash)	
		570145		
	SYM	PTOMS		CINES
	200 200 X			
0	Low Pain			
0	Low Pain Heartburn			
-				
-	Heartburn			

As there could be a delay of up to sixteen weeks between the patient recording an AE on the journal entry page and the investigator becoming aware of the event, the following process is proposed to facilitate timely reporting of AEs to medicine manufacturers.

- On the first working day of each month, patientMpower Ltd will prepare a listing of all events reported on the journal entry page for each patient. This listing will contain the following information: date of preparation of listing, patient identification number and all reported events (with date and time) per patient.
- patientMpower Ltd will send the listing to the principal investigator at the study centre..
- The investigator will review the listing of events and compare with the medicinal treatments given to each patient and determine if any of the events recorded by patients are AEs (as defined above).
- Any AEs temporally associated with the use of a medicinal product should be reported to the manufacturers of the relevant medicinal treatments.

If an AE is associated with a Boehringer Ingelheim (BI) medicinal product, the event should be reported to the BI contact address described in section 10.3.3 of Appendix 10.3.

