2.3 Benefit-risk assessment

The patientMpower app has been used in other clinical settings (post renal transplant). The renal transplant version of the patientMpower app is now offered as standard care at the national renal transplantation centre in Ireland. It has been positively received by patients and healthcare professionals and studies of its use are ongoing.

Initial feedback from participants in the user experience surveys and clinical trial in lung fibrosis indicates that patients are willing to use the app and record spirometry at home on a very regular basis (usually daily) and that they find it helpful in managing their health. These studies are ongoing at the time of writing.

It is not expected that the study or patientMpower app will create any additional risks for IPF patients.

3. Description of design and study population

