4.1 Study observational intervention

4.1.1 Identity of study observational intervention

The study observational intervention is an electronic health diary, the patientMpower app. This has been developed specifically for patients with IPF. The patientMpower app is an electronic application downloaded to the patient's mobile phone or tablet device. The app is designed to allow the patient to report various parameters relevant to IPF and record these on a regular basis, ideally daily. The information recorded by the patient will be stored in a secure cloud system and will be available to the patient through their phone or mobile device at all times. No personal health data are stored on the phone or mobile device itself.

Patients will be asked to report measurements on the patientMpower app each day. Patient-reported measures (at a minimum) will include FVC (one reading once/day), dyspnoea, activity (steps/day), distance walked per day and compliance with IPF medication. In addition. the impact of IPF on daily life (as response to PROM questions) should be reported once every week.

Additional patient-reported measures which can be reported on the patientMpower app include vital signs (e.g. heart rate, blood pressure), temperature, pulse oximetry, cough severity, activity causing worst dyspnoea and oxygen consumption. These are optional measurements and will only be recorded where practical for the patients.

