10.3 Management and reporting of adverse events/adverse reactions

10.3.1 Definitions of adverse events

An adverse event (AE) is defined as any untoward medical occurrence in a patient or clinical investigation subject administered a medicinal product and which does not necessarily have a causal relationship with this treatment. An AE can therefore be any unfavourable and unintended sign (e.g. an abnormal laboratory finding), symptom, or disease temporally associated with the use of a medicinal product, whether or not considered related to the medicinal product.

An adverse reaction (ADR) is defined as a response to a medicinal product which is noxious and unintended. Response in this context means that a

causal relationship between a medicinal product and an adverse event is at least a reasonable possibility. ADRs may arise from use of the product within or outside the terms of the marketing authorisation or from occupational exposure. Conditions of use outside the marketing authorization include offlabel use, overdose, misuse, abuse and medication errors.

A serious adverse event is defined as any AE which

- results in death,
- is life-threatening,
- requires in-patient hospitalization, or
- prolongation of existing hospitalisation,
- results in persistent or significant disability or incapacity
- is a congenital anomaly/birth defect

Life-threatening in this context refers to a reaction in which the patient was at risk of death at the time of the reaction; it does not refer to a reaction that hypothetically might have caused death if more severe.

Medical and scientific judgement should be exercised in deciding whether other situations should be considered serious reactions, such as important medical events that might not be immediately life threatening or result in death or hospitalisation but might jeopardise the patient or might require intervention to prevent one of the other outcomes listed above. Examples of such events are intensive treatment in an emergency room or at home for allergic bronchospasm, blood dyscrasias or convulsions that do not result in hospitalisation or development of dependency or abuse. Any suspected transmission via a medicinal product of an infectious agent is also considered a serious adverse reaction.

10.3.2 Adverse event and serious adverse event collection and reporting to regulatory authorities and ethics committees.

The investigator shall maintain and keep detailed records of all AEs in their patient records.

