4.2 Safety

All observed adverse events were listed.

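### Adverse events are defined only by medicine use, so the plan cannot identify events related to the app or the daily home spirometry

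*Protocol*

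**What the plan says.** Protocol 4.1.1 identifies what is being studied: "The study observational intervention is an electronic health diary, the patientMpower app". The SAP summary table widens this to the app together with the home spirometer, used daily. Protocol 3.1 says that the study changes nothing else in the patients' therapy.

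The AE definition is the same in Protocol 8.4 and in 10.3.1: "An adverse event (AE) is defined as any untoward medical occurrence in a patient or clinical investigation subject administered a medicinal product". Its second sentence extends to signs, symptoms or disease "temporally associated with the use of a medicinal product, whether or not considered related to the medicinal product".

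Under 8.4 the app owner lists all journal entries each month and sends the listing to the principal investigator, who is to "compare with the medicinal treatments given to each patient and determine if any of the events recorded by patients are AEs (as defined above". AEs then go to the makers of the medicines taken, whatever the cause. Protocol 10.3.2 adds record-keeping in patient notes and reporting to regulators and ethics committees.

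On the device itself, Protocol 5.2 says "It is not anticipated that any safety issues will arise from use of the patientMpower app or the Spirobank Smart spirometer", and Protocol 2.3 says "It is not expected that the study or patientMpower app will create any additional risks for IPF patients". SAP 4.2 consists of one sentence: "All observed adverse events were listed". The SAP gives no AE definition of its own.

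**The concern.** An AE definition should at least cover what the study asks participants to do. This one covers usual-care medicines, which the study does not change, and leaves out the app and the unsupervised daily forced expiration, which it introduces. The review step follows the same line, since the only comparator for a journal entry is the patient's medication.

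What is at stake is the safety statement. The protocol expects no added risk from the app or spirometer, and the SAP produces an AE listing. If the process never asks whether an event was related to the device, a listing with no device-related events does not show that none occurred.

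**Working it through.** The plan states no figure on this point, so the check is a reading of every safety provision against the definition of the intervention, followed by a simple exposure count.

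**Step 1. Is there a wider definition elsewhere?** Protocol 4.2.1, 5.2, 7.3.3, 8.4 and 10.3, and SAP 4.2, were read for one. None defines a device-related or procedure-related event. The end-of-study items in Protocol 6.2.4 ask about IPF exacerbations and IPF hospitalisations, not about events during spirometry.

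**Step 2. Trace one event through the rules.** Take a faint during a home blow, entered in the app journal.

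| Step | Participant taking no medicinal product | Participant taking a medicinal product |
|---|---|---|
| Reaches the investigator in the monthly listing (8.4) | Yes | Yes |
| Meets the AE definition (8.4, 10.3.1) | No | Yes, by timing, whatever the cause |
| AE record in patient notes (10.3.2) | Not required by this rule | Required |
| Regulators and ethics committees (10.3.2) | Not covered | Covered, under applicable law |
| Medicine manufacturer (8.4) | Not applicable | Yes |
| Spirometer manufacturer | No route | No route |
| App owner | Sees the raw entry | Sees the raw entry, not the investigator's assessment |
| Asked whether related to spirometer or app | No | No |
| SAP 4.2 listing | Not covered | Listed, without a device label |

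The last row assumes that the SAP uses the protocol's definition, because it states no other.

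**Step 3. Can the first column occur?** The definition refers to any medicinal product. Protocol 4.3 allows for patients receiving no IPF medicine, and 4.2.2 places no restriction on other treatments. The documents therefore do not exclude a participant on no medicine at all, but they do not show that one was enrolled. The second column does not depend on this.

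**Step 4. Potential exposure.** The inputs are one reading per day (Protocol 4.1.1 and 10.2), a window of 16 ± 8 weeks, that is 8 to 24 weeks (Protocol 6.1), and 20 patients in the treated dataset (SAP summary table).

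- Per patient: 8 × 7 = 56 to 24 × 7 = 168 manoeuvres.
- Treated dataset: 20 × 56 = 1,120 to 20 × 168 = 3,360 manoeuvres.

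This assumes full adherence and follow-up inside the planned window. It measures opportunity for events and says nothing about how often they happen.

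**The case against.** The strongest reply is that capture is better than the definition suggests, and most of that reply stands.

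- A reader might infer that device events are lost. They are not lost if journalled: the monthly listing holds every entry, with no condition on medication. What the definition restricts is the AE label and the duties that follow from it.
- A reader might infer that reports go only to drug manufacturers. Section 10.3.2 also requires patient records and reporting to regulators and ethics committees. These duties attach to AEs as defined in the same appendix, so they do not help the unmedicated participant, and they add no question about the device.
- A reader might infer that the app owner is outside the route. It compiles the listing and sees each entry first; it lacks only the investigator's judgement.
- A reader might take Protocol 4.3 as proof that unmedicated patients took part. It shows only that some may take no IPF medicine.
- The causality text in 10.3.3 belongs to the section on the funder's products. It should not be read as a study-wide causality question, whether adequate or inadequate.

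It is also fair to say that the study has no safety endpoints and no planned safety analysis, and that neither document claims the listing will demonstrate that home spirometry is safe. That limits the weight of the point. It does not supply the missing relatedness question or the missing route to the spirometer manufacturer.

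**Conclusion.** The point holds in a limited form. The AE definition and the monthly review are tied to medicines, while the intervention is an app and a spirometer. A spirometry-related event in an unmedicated participant is not an AE. In a medicated participant it is an AE and is listed, but cannot be told apart from any other event. The SAP 4.2 listing therefore cannot identify device-related events and cannot be used to support the expectation of no added risk.

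The documents do not support the stronger conclusions that such events go unseen, that the listing will be presented as clean safety evidence, or that any harm occurred.

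The change is worth making but of modest weight: a single-arm pilot with 21 consented and 20 treated patients, no safety endpoints, and no effect on any efficacy result. The conclusion assumes that the rules were followed as written and that the SAP inherits the protocol's definition. If the investigator in practice recorded events more widely, the documents do not say so.

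**What to change.** **Protocol 8.4 and 10.3.1.** Define an AE as any untoward medical occurrence in a study participant from consent to end of follow-up, whether or not a medicinal product is taken. Add one yes/no field to the existing monthly review: *related to home spirometry or the app*. Send events marked yes, with the investigator's assessment, to the spirometer manufacturer and the app owner, in addition to the existing routes.

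**SAP 4.2.** Follow-up closed on 30 April 2020 for the last two patients, so the field can now be applied only retrospectively. State which AE definition was used, re-review the stored journal entries with the new field, list events by it, and give the recorded number of home manoeuvres beside the listing. SAP 4.3 already has the frequency of recording analysed, so that count needs little new work. If the re-review is not done, state that the listing cannot support a conclusion on device safety.

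**Cost.** Wording in two protocol sections and one SAP section, one field, a somewhat longer AE listing that may include trivial events, and some retrospective review. Entries deleted at a patient's request (Protocol 8.3.3) could not be re-reviewed, and any such gap should be stated.
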